**Figure 6**  
Reveal LINQ

of their transmitter during the programmed daily transmission time. Battery life is approximately 3-years, and devices are conditionally approved for use with MRI. The incidence of device related complications is minimal and includes infection (1.2%), device migration, and pain at the implant site (<1%). Since the device is leadless, the vast majority of infections are local and treatable with oral antibiotics or device extraction (an in-office procedure). Bacteremia is an extremely rare complication. To wit, out of 66 HD patients implanted in MiD, there was only 1 definite infection and one possible implantation-related infection. Neither were bacteremic and both were successfully treated with antibiotics without device extraction. Thus, MiD data supports device safety and minimal risk of bacteremia or serious device associated infection in HD patients, regardless of dialysis access type. Out of an abundance of caution patients with history of multiple infections or immune deficiencies will nevertheless be excluded from participation in Study A and B

**Point-of-care Testing (POC)**—POC testing will be performed at each dialysis session with dialysate K or HCO3 adjusted accordingly by algorithm. POC testing allows for real-time recognition of extreme excursions in HCO3 and K and immediate dialysate manipulation as needed to maximize safety. It also ensures maximization of differences in serum-dialysate K gradients between tested algorithms while avoiding use of low K dialysate when serum potassium is already low. Further, POC at each session provides the necessary data to

**Figure 7** Abbott i-STAT system and cartridges

evaluate the achieved gradient between serum and dialysate with each strategy, to analyze association of the achieved gradient with arrhythmia, and to specifically assess for interaction between ambient serum and dialysate potassium in terms of CSA risk. Finally, POC testing allows evaluation of the extent to which POC-guided prescription differs from care in which dialysate choice is based on monthly measurement alone as assessed by the % of sessions in which management differs.

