## II. Specific Aims

Overview of Trial Design—The overall goal for these trials is to provide the data necessary for the design of definitive clinical trials. Specifically, we aim to test recruitment feasibility, the feasibility of POC electrolyte measurement and POC-directed management of the dialysis prescription, and to provide preliminary estimates of effect size with manipulation of UF rate, dialysate K, and dialysate HCO3. We will perform two related, randomized cross-over trials; Study A- dialysate interventions trial, consisting of 2 dialysate potassium interventions and 2 dialysate bicarbonate interventions (4 total cross-over interventions); and Study B-ultrafiltration rate intervention trial, consisting of 2 separate ultrafiltration rate strategies.

The central hypothesis underlying Study A and Study B is that the risk of clinically significant arrhythmias in HD patients can be reduced by altering components of the dialysis prescription.

**Aim 1—To test the feasibility and safety of POC-guided dialysate prescription adjustment and the feasibility of limiting UF rate in HD patients.** The current studies will pilot our educational strategies and the dialysate potassium, dialysate bicarbonate and UF intervention strategies to test their feasibility in a multi-center setting. They will test the hypothesis that  $\geq 80\%$  adherence with proposed interventions is feasible, and that the safety need for unscheduled dialysis or severe abnormalities in potassium and bicarbonate will be minimal.

**Aim 2—To assess recruitment feasibility and retention rate for trials combining ILR insertion to monitor arrhythmia and interventions using POC-guided dialysis prescription or UF rate manipulation.** Screen failures and retention rates will be captured and analyzed. Whether recruitment rates  $\geq 1$  patient per month and retention rate  $> 90\%$  are achievable in each study will be tested.

**Aim 3—To refine effect estimates of the change in monthly CSA duration during Study A (dialysate potassium intervention to maximize vs. minimize intradialytic potassium removal) and Study B (aggressive vs. conservative ultrafiltration rate).** Refining estimates of change in CSA with each pair of interventions will provide key information necessary for design of definitive trials. Whether CSA decreases with minimization of potassium removal, alkalosis limitation and UF rate minimization will be tested.

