POC-HCO3 results will be obtained prior to each HD session and will inform the selection of the dialysate HCO3 concentration. As with potassium, POC-testing allows dialysate HCO3 concentration to be matched according to serum HCO3 and has analogous advantages in terms of safety, achieved gradient, and potential analyses, compared to a design using fixed dialysate concentrations. The algorithm has been designed based on published data on the expected post dialysis increases in serum HCO3 and overall time-averaged serum HCO3 expected from any given combination of pre-dialysis serum and dialysate HCO3 concentrations. As shown in the table, excellent separation of dialysate and serum HCO3 concentrations are expected.

Dialysate Bicarbonate Intervention Algorithm				
POC HCO 3 (mEq/L)	Dialysate HCO 3 (mEq/L)	Gradient (mEq/L)	Expected Change in post HD HCO 3	Expected Time Avg HCO 3
Acidosis Avoidance				
<20	40	≥20	[contact]-18	[contact]	33	6-8	negligible rise	26
≥28	26	≤ -2	negligible decrease	26
Alkalosis Avoidance				
<20	36	≥16	[contact]	7-11	[contact]	-1-3	negligible rise	24
≥28	20	≤ 16	negligible decrease	26

**Overview of Ultrafiltration (UF) Trial- Study B**—The UF rate intervention will use identical inclusion/exclusion criteria as the dialysate Intervention trial with a few exceptions. Subjects are required to have an interdialytic weight gain necessitating an UF rate of ≥13 mL/kg/hour of dialysis to achieve the target post-dialysis weight in ≥6 dialysis sessions in the month prior to enrollment. This criterion is necessary to achieve separation in UF rates between the aggressive and restricted UF rate periods. Conversely, there will be no exclusions on the basis of baseline hemoglobin or serum potassium concentration since point of care testing of electrolytes is not be required and the UF intervention is not expected to impact serum potassium concentration.

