**Adherence Endpoints**—Adherence will be assessed for each of the 4 dialysate interventions (K removal minimization vs. maximization, acidosis vs. alkalosis avoidance) as the % of sessions in which POC testing is completed and the dialysate is adjusted according to the algorithm. For the UF trial, it will be assessed as the % of sessions in which the mandated UF rate is delivered. We hypothesize that 90% adherence is achievable. HD staff will be anonymously surveyed once 3 subjects have completed 1 month of each trial and once 6 patients have completed each trial. A questionnaire will identify the impact of time constraints, patient refusal, algorithm complexity, inadequate training on POC devices, clinical concerns, or other factors on protocol adherence. Face-to-face review with HD staff will facilitate identification of other barriers. Where addressable factors are identified, they will be corrected for remainder of the trials. Since the overall goal is to assess implementation feasibility, secondary analyses will compare pre- and post-correction adherence in addition to estimating overall adherence. This adaptive plan will facilitate identification of best practices and ensures that estimates represent the feasibility of subsequent protocols to be implemented after incorporating lessons learned in the pilot experience.

**Secondary Feasibility Measures**—POC electrolyte measurements will be compared with usual care monthly labs to assess accuracy of POC testing. An additional metric that will be used to determine the impact of POC testing on trial design will be the percent of sessions in which the POC-guided dialysate prescription differs from a hypothetical prescription in which the choice of dialysate is based solely on the once-monthly lab.

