**Effect Estimates (Aim 3)**—Estimating the mean and standard deviation (SD) of the change in duration of clinically significant arrhythmia (CSA) per month is critical for power and sample size calculation and planning definitive studies. The total monthly duration of CSA (in minutes) will be utilized as the primary efficacy endpoint in comparing each pair of interventions (K removal maximization vs. minimization, acidosis vs. alkalosis avoidance, aggressive vs. conservative UF). In the event of incomplete follow-up, CSA duration will be indexed to follow-up time. CSA will be defined on the basis of arrhythmias likely to lead to SCA or serious morbidity and mortality and will include AF, asystole  $\geq 3$  seconds, bradycardia  $\leq 40$  beats per minute lasting  $\geq 6$  seconds, and sustained VT  $\geq 130$  beats per minute lasting  $\geq 30$  seconds. CSA's will be adjudicated by study electrophysiologists.. Currently, no data exists on the expected impact of the interventions on CSA duration, but given a mean duration of CSA in MiD of  $356 \pm 1765$  minutes, a sample size of 20 subjects provides 80% power for detection of change in CSA duration of 140 minutes/month given within-subject correlation of 0.9, 370 minutes for within-subject correlation of 0.7, and 470 minutes if within-subject correlation is 0.5.

**Statistics and Analysis**—A balanced, uniform crossover design will be used with randomization stratified by site in blocks of 4.

**Adherence** will be estimated as % (95% CI) of sessions without protocol deviation. Comparison of adherence percentage pre- vs. post-interim analysis of adherence will be made using linear regression with time period as an independent variable. Exploratory analyses will assess association of adherence with site, dialysis shift (1st-3rd), and day (Monday/Wednesday/Friday or Tuesday/Thursday/Saturday).

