Study procedures ensure testing of electrolytes at each session (3x/week) in contrast to a frequency of as little as 1x/month in routine practice. Severe electrolyte abnormalities will thus be recognized earlier with study patients than in routine practice. Similarly, POC testing will ensure that the dialysis prescription will be adjusted according to the ambient potassium or bicarbonate at that dialysis session. In routine practice, follow-up testing at outpatient dialysis units typically has a turn-around time of hours (stat testing) or days (routine lab draws) which makes appropriate adjustment of the dialysis prescription unfeasible. Thus, study procedures may actually lower the risk of severe electrolyte abnormalities or risk of complications from those abnormalities. However, significant inaccuracy in the point of care testing results could modify the associated risks.

To further mitigate risk, patients with severe abnormalities in potassium ( $K>6.5$  or  $<3.0$ ) or bicarbonate ( $<20$  or  $>32$ ) will temporarily come off therapy and be treated off-protocol at the discretion of their clinician.

**Study B UF algorithms** are designed to either limit UF rates to  $\leq 10$  mL/kg/hour or to allow UF rates  $\geq 13$  mL/kg/hour. As discussed in the research summary, there is significant equipoise regarding the risk/benefit ratio of either strategy, as the use of high UF rates minimizes the risk of volume overload at the expense of rapid fluid shifts, whereas limiting UF rate minimizes the risk of rapid fluid shifts at the expense of increasing the risk of volume overload. Both strategies are routinely employed in clinical care. Thus, it is again unclear whether research-related risks are materially different than those in routine practice. As described in the Research Plan, subjects will cross over weekly between the unlimited and restricted UF treatments, thereby allowing removal of excess fluid accumulated during the restrictive week during the subsequent, unlimited week. This will limit any excessive fluid gains to a maximum of a few liters over the course of the restricted UF week thereby limiting the possibility of volume-related complications in the event patients fail to self-regulate intake of salt and water. Safety, will be further ensured because patients who show signs of significant volume overload will have the

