#### **Protections Against Risk**

Individuals at increased risk of adverse events from study treatments (such as those with infection, severe hyperkalemia, or anti-coagulation that prevents safe ILR implantation) will be excluded. Patients will be monitored for adverse effects with a follow-up examination of the device incision/pocket 1 and 4

weeks after ILR insertion, and we will have at least monthly review for adverse events thereafter. In addition, due the nature of chronic dialysis, all patients will be seen regularly by other medical personnel approximately 3x/week throughout the course of the study which should allow prompt recognition and response to adverse events. Individuals experiencing significant adverse events (e.g. volume overload requiring or severe electrolyte abnormalities) will have study intervention halted until these conditions can be fully-treated clinically at which point consideration to resumption of protocols can be considered if clinically appropriate (and DSMB review does not suggest modification or termination of the study). In addition, in the event of immediately life-threatening arrhythmias (e.g. ventricular fibrillation, sustained VT, symptomatic asystole, or sustained AF) identified on review of ILR tracings, clinical records will be reviewed and clinical providers contacted in order to institute appropriate therapy

As reviewed above, risks associated with the study procedures are in general not significantly different than risks HD patients are exposed to during routine care and study treatments are within the range of therapies that can be considered standard clinical care and differ mostly by being protocolized, randomized and driven by POC lab results rather than by results of monthly lab testing. Additionally, there are unique, study-specific risks relating to ILR insertion and additional phlebotomy- neither of which is expected to result in significant risk to participants. No vulnerable populations will be enrolled. Pregnant individuals will be excluded given the need for ILR insertion and potential risk of impacting fetal development.

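### The Study A bicarbonate and potassium tables prescribe a dialysate at values where the safety rule takes the patient off therapy, and the plan does not say how those sessions count towards adherence

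*Combined protocol and SAP*

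**What the plan says.** **Dialysate choice.** Section V (Bicarbonate Intervention) says that POC bicarbonate results "will be obtained prior to each HD session and will inform the selection of the dialysate" concentration. Below 20 mEq/L the table gives dialysate 40 under acidosis avoidance and 36 under alkalosis avoidance. At 28 or above it gives 26 and 20, with no upper limit. The potassium table in the same section gives dialysate K 3 for serum K below 4 and dialysate K 2 for 6.4 or above, in both strategies.

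**Safety rule.** Section VII (Study A potassium and bicarbonate algorithms) says that patients with K above 6.5 or below 3.0, or bicarbonate below 20 or above 32, "will temporarily come off therapy and be treated off-protocol at the discretion of their clinician". Under Protections Against Risk, patients with significant adverse events, severe electrolyte abnormalities among them, "will have study intervention halted until these conditions can be fully-treated clinically", after which resumption may be considered if clinically appropriate and if DSMB review does not point to a change.

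**Adherence.** Section VI (Adherence Endpoints) scores each of the four dialysate interventions by the percentage of "sessions in which POC testing is completed and the dialysate is adjusted according to the algorithm". Statistics and Analysis in the same section, like the Study Summary, says that adherence "will be estimated as % (95% CI) of sessions without protocol deviation". Adherence Endpoints adds: "We hypothesize that 90% adherence is achievable". Aim 1 in section II sets the hypothesis at 80% or more.

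**The concern.** Two instructions apply to the same POC value. Dialysis staff enter the dialysate by hand from the algorithm, while the rule that removes the patient from therapy sits only in the risk section. Two sites could deliver different dialysate at the same value and each point to protocol text in support.

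The conflict carries into the feasibility endpoint. Adherence is what Aim 1 estimates, separately for each dialysate intervention. Under the Adherence Endpoints wording, a site that obeys the safety rule is marked non-adherent whenever the clinician's dialysate differs from the table. Under the other wording the result depends on whether such a session is logged as a deviation. Whether a strategy reaches 80% or 90% could then reflect a scoring choice made after the data are in, and not how well staff delivered the algorithm.

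**Working it through.** The plan gives no figure of its own here, so there is nothing to reproduce. The check has three steps.

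**Step 1: the two instructions side by side.** Only table rows that are legible in the public text are used.

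| POC value (mEq/L) | Dialysate in table | Safety rule | Both can be followed? |
|---|---|---|---|
| HCO3 <20 | 40 or 36 | off therapy | No (whole row) |
| HCO3 28 to 32 | 26 or 20 | none | Yes |
| HCO3 >32 | 26 or 20 | off therapy | No |
| K <3.0 | 3 | off therapy | No |
| K 3.0 to <4 | 3 | none | Yes |
| K 6.4 to 6.5 | 2 | none | Yes |
| K >6.5 | 2 | off therapy | No |

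The bicarbonate table and the rule use the same cut-off of 20, so one complete row in each strategy is both prescribed and withdrawn. No sentence in the protocol gives precedence.

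**Step 2: how a session at such a value is scored.**

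| What happens | Adherence Endpoints wording | Statistics and Analysis wording |
|---|---|---|
| Safety rule followed, dialysate differs from table, not logged as a deviation | Fail | Pass |
| Safety rule followed, dialysate differs from table, logged as a deviation | Fail | Fail |
| Safety rule followed, clinician happens to choose the table value, not logged as a deviation | Pass | Pass |
| Table followed, safety rule ignored, breach logged as a deviation | Pass | Fail |

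The definitions disagree in the first and last lines. In the second they agree, and both penalise the site for obeying the safety rule. The plan does not say which line applies, or whether these sessions leave the denominator.

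**Step 3: illustrative size.** Inputs:
- 20 subjects per trial (section V) and 12 scheduled sessions per period (Description of Study Visits), so 20 × 12 = 240 scheduled sessions per strategy.
- Share s of sessions under the safety rule: not in the documents; assumed 2%, 5%, 10% or 20%.
- Delivery d in all other sessions: assumed 95%.

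Adherence is d(1 − s) if safety-rule sessions count as failures, d(1 − s) + s if they count as passes, and d if they are excluded.

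| s | Sessions of 240 | Failures | Passes | Excluded |
|---|---|---|---|---|
| 2% | about 5 | 93.1% | 95.1% | 95% |
| 5% | 12 | 90.25% | 95.25% | 95% |
| 10% | 24 | 85.5% | 95.5% | 95% |
| 20% | 48 | 76.0% | 96.0% | 95% |

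For example, at s = 10%: 0.95 × 0.90 = 0.855, and 0.855 + 0.10 = 0.955.

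Counted as failures, adherence falls below 90% once s exceeds 1 − 0.90/0.95 = 5.3%, which is 13 of 240 sessions, or 13/20 = 0.65 per subject. It falls below 80% once s exceeds 1 − 0.80/0.95 = 15.8%, which is 38 sessions.

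**The case against.** The strongest reply is that the safety rule plainly overrides the tables: it is introduced as further risk mitigation and repeated under Protections Against Risk. That is the natural reading, and the fix adopts it. It does not settle the matter, because the lowest bicarbonate rows would then have no use, while section I presents POC testing at extreme values as allowing "immediate dialysate manipulation as needed to maximize safety". Nor does it say how the sessions are scored.

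A second reply is that few sessions may be affected. Aim 1 expects severe potassium and bicarbonate abnormalities to be minimal, and at a 2% share every scoring choice stays above 90%. This stands, so the figures above are not a forecast. Against it, HCO3 below 20 or above 32 is itself a named safety endpoint, Study A sets no bicarbonate limit at entry, and a halt lasting until the abnormality is treated could cost more than one session.

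Third, the analyses are declared exploratory, the 80% and 90% figures are hypotheses with no go/no-go rule attached, and either score can be computed later from the POC value and the delivered dialysate. This limits the consequence but leaves the contradictory bedside instruction in place.

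Two stronger inferences are not supported. A reader might infer that alkalosis avoidance would suffer more because its dialysate is lower. But off therapy the clinician chooses the dialysate, and the trigger above 32 could act more on the higher-dialysate strategy, so the net direction cannot be known from the documents. A reader might also infer that there is no rule for resuming; Protections Against Risk gives a clinical one.

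**Conclusion.** The conflict between the tables and the safety rule is on the page and needs no assumption. It covers the whole HCO3 <20 row, the part of the ≥28 row above 32, and the K values above 6.5 and below 3.0. This is an internal inconsistency, not an arithmetic error.

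The effect on adherence is conditional. It is tempting to conclude that the two definitions must score a safety-rule session in opposite ways. The documents support only that they can: the clinician's dialysate must differ from the table, and following the safety rule must not be logged as a deviation. If it is logged as one, the definitions agree and both mark the site down for complying.

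The size is unknown because the share of such sessions is not given. Under the assumed 95% delivery elsewhere, the gap between counting these sessions as failures and as passes equals their share, so it is 2 to 20 percentage points over the range shown. The correction should be made, mainly because it removes a contradictory instruction to staff and fixes the Aim 1 endpoint at almost no cost.

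**What to change.** **(a) Precedence.** State in section V that the off-therapy rule overrides both dialysate tables, and edit the tables to match. HCO3 below 20 and above 32, and K above 6.5 and below 3.0, become off protocol with the clinician's choice of dialysate; the ≥28 bicarbonate row becomes 28 to 32. If the investigators do intend 40 or 36 to be given below 20, change the bicarbonate trigger in section VII instead, with DSMB agreement. Resumption can stay as written under Protections Against Risk.

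**(b) One adherence definition in section VI**, repeated in the Study Summary: sessions with the POC test completed and the table dialysate delivered, divided by attended sessions that are not off protocol under the safety rule. Beside it, report the number and share of safety-rule sessions by strategy, and run one sensitivity analysis that counts them as non-adherent. Excluding them without this would hide how often the algorithm cannot be delivered, which section VI treats as critical to scaling up.

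**Cost.** An amendment with DSMB notice, covering a few table cells, one precedence sentence and one definition, plus one extra reported share and one sensitivity figure. No new visits, samples or patients are needed, because the POC value and the delivered dialysate are already required to score adherence at each session.
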